Improving Vision in Adults With Macular Degeneration, Study 1: the Effect of Brain Stimulation

Study Protocol Outline

Date Approved by Researchers: September 19, 2019

Inclusion Criteria

- Diagnosis of AMD (age 60+) or JMD (current age 18+).
- Central vision loss and use of a PRL (confirmed by a microperimeter).
- Visual acuity (VA); between 0.5 and 1.0 logMAR inclusive (6/18-6/60) in the better eye.
- Best-corrected near visual acuity of 4.0M at 40 cm or better in the better eye
- Stable vision for the previous 3 months (by patient report).

Exclusion Criteria

- Diagnosed dementia.
- Not fluent in reading English (Waterloo) or Chinese characters (Hong Kong).
- any ocular surgery (including anti-vegF injections) within the duration of the study.
- Ocular pathology other than JMD or AMD that can reduce central vision.
- Severe hearing impairment.

Contraindications for tDCs:

- Suffer from epilepsy, have had an epileptic seizure, or family history of epilepsy.
- Any metal implant (excluding tooth fillings).
- Implanted medication pump or implanted electronic device, including pacemaker or defibrillator
- Heat disease, neurological condition, or have had neurological or cardiac surgery.
- Recurring headaches
- Skull fracture or head injury
- Head or Brain surgery
- Pregnancy
- Skin Condition
- Taking any medication on the list on Form A
- Excessive alcohol (>2 standard drinks) or slept dramatically less the usual in the last 24 hours.

Protocol Outline

Day 0: Pre-Screening

1. Potential participants are recruited
 - Done by clinician for privacy and also to make an initial assessment about eligibility.
 - Diagnosis of AMD or JMD with VA in the inclusion range
 - Age ≥ 18
 - No diagnosis of dementia
 - No other eye disease or condition affecting vision
 - No indication of being not fluent reader in tested language
2. Call potential participants to recruit.

Day 1: Screening and RSVP baseline selection

1. Consent form and signature
2. Refraction
3. Distance ETDRS acuity.
4. Near VA (MNREAD with stopwatch) and with +4D in trial frame).
5. Decide on eye to be used (eye with better near reading vision)
6. Ocular health check (of the eye to be used)
7. PRL measure with microperimetry
8. If better eye has another ocular disease or not a stable PRL, check the poorer eye for eligibility and use that for all further testing

If patient qualifies for main study:

10. Full RSVP test [45+ minutes]
 - 5 print sizes by 5 reading speeds, selected based on the MNREAD test results.
11. Select single print size and word speed combination that is predicted to elicit 55% with the following procedure:
 - Fit a two-line function and a simple linear regression to the data
 - i. If two-line fit is better (a CPS/ “elbow” was found):
The CPS defines the print size and word speed to be used
 - ii. If simple linear regression is better (no reliable “elbow” found):
Use print size of 1.5 deg x-height and corresponding reading speed
12. Blind-selection of stimulation codes to determine active/sham schedule for participant
 - Active/sham stratified by:
 - i. VA – [0.5, 0.8) and [0.8, 1.0] logMAR groups, to be balanced as far as stimulation schedule

NOTE: JMD participants will not be stratified by VA, but active/sham schedules will be balanced for JMD participants.

Treatment Days: *(treatment days must be separated by 2 – 14 days, otherwise redo baseline measures.)*

- Order of crowded and uncrowded tests is randomized on a per-subject basis but maintained throughout testing for each patient.
 - Setup consists of two computers. One computer 3 meters away for the crowded and uncrowded Landolt C test, and one computer on an independently rolling cart. The RSVP task will be done on the rolling computer, and then will be moved out of the way for the participant to do the Landolt C tests. This allows older patients to not be required to move continuously for these tests.
1. Primary outcomes pre-test.
 - a. specifically-selected RSVP condition tested.
 2. Secondary outcomes pre-test. Computer is fixed 3 meters away.
 - a. Crowded Landolt C
 - b. Uncrowded Landolt C
 - c. Manually calculate measure of crowding strength:
 3. Stimulation (either active or sham) for 20 minutes.
 - a. During stimulation: specifically-selected RSVP condition tested
 - b. During stimulation: Crowded and Uncrowded Landolt C
 4. Five minutes after stimulation end:
 - a. Specifically-selected RSVP condition tested
 - b. Crowded and Uncrowded Landolt C tested
 5. Thirty minutes after stimulation end:
 - a. Specifically-selected RSVP condition tested
 - b. Crowded and Uncrowded Landolt C tested

6. Participant fills out a brain stimulation adverse-effects questionnaire.
7. ONE THE FINAL TREATMENT DAY: administer blind MoCA cognitive test for use in sensitivity analysis/as a covariate
8. After sending patient home, use custom-written program to process all patient data collected for that day for the individual subject.

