NCT04111068

Official Title: Improving Vision in Adults With Macular Degeneration, Study 1: the Effect of Brain Stimulation

Date Last Updated: February 4, 2022

Statistics Analysis Plan

Planned Study Components

- A. Independent Variables:
 - 1. Stimulation Type (active vs sham)
 - 2. Test Time (effect during, effect 5 mins post, effect 30 mins post)
 - For statistical testing, Test time will contain 3 levels, defined as:
 - i. During stimulation baseline
 - ii. 5 mins post stimulation baseline
 - iii. 30 mins post stimulation baseline
- B. Experimental Design and Outcome Measures:
 - 1. 2 (Stim type) x 3 (Test time) analysis: Outcome is Crowded VA in logMAR (FrACT)
 - 2. 2 (Stim type) x 3 (Test time) analysis: Outcome is Uncrowded VA in logMAR (FrACT)
 - 3. 2 (Stim type) x 3 (Test time) analysis: Outcome is RSVP reading analysis
- C. *Interactions:* An interaction between stim type and test time indicates that active stimulation was effective, but not at every timepoint. Therefore, the planned contrast in the event of an interaction:
 - 1. Active vs. sham: individually compare active vs sham at the three timepoints.
- D. Covariates to examine:
 - 1. Language, primary analysis (dichotomous)
 - 2. Age (continuous)
 - 3. Distance visual acuity (will be dichotomized)^a
 - 4. RSVP critical print size (will be dichotomized)^a
 - 5. RSVP maximum reading speed (will be dichotomized) ^a
 - 6. Cognitive Screening: MoCA-blind (UW) and (HKPU) (will be dichotomized) ^b
 - 7. Type of AMD: wet, dry (dichotomous) ^c
 - a. Because the different languages likely elicit different mean performances, covariates listed will be dichotomized with a median split separately for each language to allow combined data analysis with the included covariate. The "low" group will include any participants scoring the median. The "high" group will include only participants scoring better than the median.
 - b. Cognitive Screening will be dichotomized separately for each language along standard thresholds for clinical significance. This covariate will only be tested if at least 5 total participants are allocated to both groups.
 - c. Type of AMD will only be tested if at least 5 total participants are allocated both groups.
- E. Additional Details:
 - 1. The analysis will be run individually for each planned outcome measure.
 - 2. Participants with incomplete data will be excluded from the analysis
 - 3. All tests will be 2-tailed with alpha = 0.05

Analysis Procedure

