- 1. Normality check: Check if ANOVA assumptions are violated (languages combined)
 - 1. Sphericity of variances use Mauchly's Test of Sphericity to check for significant violations of sphericity.
 - Normality of Residuals visually inspect pp plot and qq residual plots evaluate the degree of violation.
 - If sphericity assumption is violated: Use Greenhouse Giesser correction for all main effects and interactions, following *Parametric Statistics*, section 2a
 - If interaction between independent variables is significant: Use Wilcoxonsigned-rank tests for planned pairwise comparisons instead of ttests.
 - If normality assumption is violated: follow *Nonparametric Statistics*, section 2b.

2a. Parametric Statistics

- 1. Primary Analysis:
 - i. Perform repeated-measures ANCOVA, with Language as covariate.
 - If interaction between stimulation type and test time is significant:
 - ii. Examine planned comparisons with within-subject ttests

If language covariate is significant or significantly interacts with another factor:

iii. Run separate repeated-measures ANOVAs for each language

If either ANOVA reveals an interaction:

- iv. Examine planned pairwise comparisons with within-subject ttests
- 2. Secondary Analysis:
 - i. Perform repeated-measures ANCOVA, iteratively with each secondary covariate to be tested.

If interaction between stimulation type and test time is significant:

ii. Examine planned comparisons with within-subject ttests

If any dichotomous covariate is significant or significantly interacts with another factor: iii. Run separate repeated-measures ANOVAs for each level of the covariate

If either ANOVA reveals an interaction:

iv. Examine planned pairwise comparisons with within-subject ttests

2b. Nonparametric Statistics

- 1. Primary Analysis:
 - i. Perform aligned rank transform for nonparametric ANOVA with 3 independent factors.
 - 2 (Stim type) x 3 (test time) x 2 (language) mixed effects ANOVA

If stim type and test time interact, but language is not significant and no interaction involving language occurs:

ii. Run planned pairwise comparisons using Wilcoxon-signed-rank tests

If language is significant or if language significantly interacts with any other factor:

iii. Discard previous analysis and run two separate ART-transformed 2 (stim type) x 3 (test time) nonparametric ANOVAs, one for each level of language.

If either ANOVA reveals an interaction:

iv. Run planned pairwise comparisons with Wilcoxon-signed-rank tests

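### Age is confounded with AMD versus JMD by the entry rule, and no model in the SAP contains AMD versus JMD, so an Age or Age-by-stimulation effect could not be attributed to age

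*Protocol*

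**What the plan says.** - **Entry (Protocol, Inclusion Criteria).** "Diagnosis of AMD (age 60+) or JMD (current age 18" or older. JMD has no upper age limit, so older JMD participants are eligible.
- **Allocation (Protocol, Day 1, note to step 12).** "JMD participants will not be stratified by VA, but active/sham schedules will be balanced for JMD participants". JMD is thus its own group when schedules are balanced.
- **Covariates (SAP, Planned Study Components, D).** Item 2 is "Age (continuous"). The only disease variable, item 7, is "Type of AMD: wet, dry (dichotomous"), which has no JMD level. Note c adds a condition: "Type of AMD will only be tested if at least 5 total participants are allocated both groups". Note b sets the same minimum for the cognitive screen.
- **Models (SAP, Analysis Procedure, 2a).** Primary: "Perform repeated-measures ANCOVA, with Language as covariate". Secondary: "Perform repeated-measures ANCOVA, iteratively with each secondary covariate to be tested". The nonparametric branch (2b) also takes covariates one by one. If stimulation type and test time interact, the follow-up is "Examine planned comparisons with within-subject ttests".
- **Exclusions (SAP, E, item 2).** Only incomplete data remove a participant, so JMD participants are pooled by default.
- **JMD in the SAP.** It appears only as a category in the descriptive table with one row per participant.

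**The concern.** Below 60 there are no AMD participants, so in that part of the age range nothing separates age from disease. Because each secondary covariate is fitted alone, Age is never adjusted for diagnosis. The planned split by covariate level applies only to dichotomous covariates, so no follow-up step would show that an Age signal came from the JMD group.

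Pairing active with sham within each person removes a difference in overall performance between the diseases. It does not remove a difference in how the two diseases respond to stimulation, and an Age-by-stimulation term would pick that up. At stake is a possible statement that response to stimulation changes with age, when the data might only show that JMD and AMD respond differently, perhaps on the strength of a few young participants with high leverage.

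**Working it through.** The plan gives no figure to reproduce: no sample size, JMD share, age distribution or effect size. The structure comes from the documents; every numerical input below is an assumption, shown over a range.

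**Step 1: how much of Age is diagnosis?** Let p be the JMD share, D the gap in mean age, and SD_A and SD_J the SDs of age in AMD and JMD. The share of Age variance lying between diagnoses is

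η² = p(1−p)D² / [p(1−p)D² + (1−p)SD_A² + p·SD_J²].

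Two examples:

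- JMD 35 (SD 10), AMD 78 (SD 8), p = 0.2: between = 0.16 × 43² = 295.8; within = 0.8 × 64 + 0.2 × 100 = 71.2; η² = 295.8/367.0 = 0.81.
- JMD 65 (SD 12), AMD 75 (SD 8), p = 0.1: between = 0.09 × 10² = 9; within = 0.9 × 64 + 0.1 × 144 = 72; η² = 9/81 = 0.11.

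| Assumed mean age (SD) | p = 5% | 10% | 20% | 30% | 50% |
|---|---|---|---|---|---|
| JMD 35 (10), AMD 78 (8) | 57% | 71% | 81% | 84% | 85% |
| JMD 45 (15), AMD 78 (8) | 42% | 55% | 64% | 67% | 65% |
| JMD 55 (15), AMD 75 (8) | 21% | 31% | 40% | 43% | 41% |
| JMD 65 (12), AMD 75 (8) | 7% | 11% | 17% | 19% | 19% |

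With no JMD participants the share is 0%. With ages spread evenly (AMD 60-95) over the same values of p, it is 40-75% for JMD aged 18-60 and 15-30% for JMD aged 18-95. The assumed JMD ages drive the result more than the JMD share does.

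**Step 2: what would the Age test then do?** A simulation (4,000 runs per setting) regressed one active-minus-sham difference per person on Age. Age had no effect; JMD shifted the difference by 1 SD. Ages were AMD 78 (SD 8), held within 60-95, and JMD 45 (SD 15), held within 18-90. The table shows how often Age was significant at two-sided 0.05.

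| N | JMD | Age alone | Age plus AMD/JMD |
|---|---|---|---|
| 20 | 2 | 16% | 5.2% |
| 20 | 4 | 28% | 4.5% |
| 20 | 6 | 35% | 5.4% |
| 30 | 3 | 21% | 4.7% |
| 30 | 6 | 39% | 5.2% |
| 30 | 9 | 49% | 5.1% |

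Fitting diagnosis alongside Age brings the rate back to about 5%. Because the outcome is already active minus sham, the diagnosis term here is a diagnosis-by-stimulation interaction. In the SAP's repeated-measures model, that interaction has to be included explicitly; a diagnosis main effect alone would not do the job. The simulation simplifies the SAP's model to one difference score, and its rates depend on the assumed 1 SD shift.

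**The case against.** The strongest reply is that this is a small matter of unknown size. Age is one of six secondary covariates; the primary model adjusts for Language only. Active and sham are compared within the same people. A significant continuous Age term triggers no further analysis, and the SAP does not commit itself to any claim about age. The descriptive table lists age and disease type for each participant, so a few young JMD participants would be visible. All of this stands and limits the point to how an Age finding is read. The table would let a reader suspect the confounding, but it would not supply an adjusted estimate.

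A second reply concerns the remedy. Added as an ordinary dichotomous covariate, diagnosis could, if significant, lead under section 2a to a separate ANOVA on two or three JMD participants. It would also sit badly with the SAP's own minimum of 5 per group: three of the six settings in step 2 (2, 3 and 4 JMD participants) fall below it. This also stands, and the fix allows for it.

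Two stronger readings are tempting. A reader might infer that the Age effect would be largely an AMD-versus-JMD contrast. That holds if JMD participants are young and not too few, but the documents fix neither their number nor their ages, and JMD has no upper age limit. A reader might also infer that disease is left out of the analysis altogether. It is not: wet versus dry AMD is a planned covariate. What is missing is AMD versus JMD.

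**Conclusion.** The confounding is built into the entry rule, and the SAP as written cannot resolve it. Its degree is not determined by the documents: the AMD-JMD difference could be anything from 0% to about 85% of Age variance across the assumptions tried. If the two diseases respond differently by 1 SD, under the assumed ages and sample sizes, Age alone would be significant in 16-49% of trials with no age effect. If they respond alike, there is no such spurious Age-by-stimulation signal from this source.

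The documents do not support extending this to bias in the active-sham contrast, since each participant serves as their own control. This is a worthwhile minor improvement: it concerns one secondary covariate, and the variable needed is already recorded.

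**What to change.** Amend the SAP as follows.

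1. Run the Age covariate analysis in AMD participants only. If enough JMD participants enrol, the alternative is to keep everyone and include an AMD/JMD term and its interaction with stimulation alongside Age.
2. Add an AMD-only sensitivity analysis of the active-sham contrast.
3. Test diagnosis as a covariate in its own right only if each group has at least 5 participants, as for wet/dry AMD and the cognitive screen. State that a diagnosis term used to adjust Age does not trigger separate ANOVAs by diagnosis.
4. State how JMD participants are handled when wet versus dry AMD is tested.

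No new data are needed. The cost is a less precise Age slope, over a narrower age range if restricted to AMD, and a few fewer participants in the sensitivity analysis. Adding diagnosis as an adjustment spends a little residual information.

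### Active/sham order is not stated to be balanced within language/site, although the SAP can fall back on per-language analyses and no model adjusts for order

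*Protocol*

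**What the plan says.** Allocation is described in the protocol under Day 1, step 12: "Blind-selection of stimulation codes to determine active/sham schedule for participant". Under the line "Active/sham stratified by", one stratification factor follows: "VA – [0.5, 0.8) and [0.8, 1.0] logMAR groups, to be balanced as far as stimulation schedule". A note adds that "JMD participants will not be stratified by VA, but active/sham schedules will be balanced for JMD participants". Neither language nor site appears. The protocol does not say whether the two sites share a code list or hold separate ones.

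Language and site coincide. The exclusion criteria read "Not fluent in reading English (Waterloo) or Chinese characters (Hong Kong".

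The design is within-person, with sessions on different days ("treatment days must be separated by 2 – 14 days, otherwise redo baseline measures"). Each treatment day begins with a pre-test of the RSVP condition and of both Landolt C tests. The tests are repeated during stimulation, then 5 and 30 minutes after it ends.

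The SAP (Planned Study Components, D) names language as the covariate for the primary analysis. The first primary analysis combines the languages, using an ANCOVA or, on the nonparametric route, an aligned rank transform ANOVA with language as a factor. If language is significant or interacts with another factor, section 2a instructs: "Run separate repeated-measures ANOVAs for each language". Section 2b does the same and discards the combined result. No model in either section contains order, sequence or period. Participants with incomplete data are dropped (Planned Study Components, E).

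**The concern.** In a crossover without a period term, balanced order is the only protection against session effects such as practice. Step 12 provides that protection by VA band and within JMD, but does not state it for language, the level at which the SAP may draw its conclusions.

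Two results are exposed. The first is the active-sham contrast within each language. The second is the stimulation-by-language interaction, which is one of the triggers for separate analyses. If order is balanced overall and the languages are of equal size, an excess of sham-first in one language forces an equal excess of active-first in the other. The two biases cancel in the pooled estimate but add in the interaction. Chance imbalance could therefore help create an apparent language difference and then bias both of the analyses run because of it.

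**Working it through.** The documents state no sample size, effect size, SD or dropout rate, so there is no figure of the plan's own to reproduce.

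**Assumptions (not in the documents).** One active and one sham day; 10, 15 or 20 participants per language; equal language sizes; one shared code list balanced overall.

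**Step 1: bias formula.** Let π be the day-2 minus day-1 difference in the analysed outcome, and τ the true active-minus-sham effect. A sham-first participant contributes τ + π and an active-first participant τ − π. Within a language of size n the expected contrast is

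τ + π × (n_SF − n_AF)/n,

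where SF is sham-first and AF is active-first. At n = 10:
- 6:4 gives (6 − 4)/10 = 0.2 of π
- 7:3 gives (7 − 3)/10 = 0.4 of π
- 8:2 gives (8 − 2)/10 = 0.6 of π

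With 7:3 in one language and 3:7 in the other, the between-language difference in the contrast shifts by 0.4 − (−0.4) = 0.8 of π. The pooled shift is 0.

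**Step 2: how often imbalance arises.** With order balanced overall, the number of sham-first participants in one language is hypergeometric (total N, N/2 sham-first, n = N/2 drawn).

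| n per language | mean absolute imbalance | P(60:40 or worse) | P(imbalance ≥ 0.4) |
|---|---|---|---|
| 10 | 0.172 | 0.656 | 0.179 |
| 15 | 0.152 | 0.466 | 0.027 |
| 20 | 0.124 | 0.343 | 0.026 |

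At n = 10 an imbalance of 0.4 is a 7:3 split.

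**Step 3: type I error given the split.** Two-sided paired t-test at 0.05 without a period term, 100,000 simulated trials per cell, π in SDs of the paired difference.

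| n, split | π = 0.25 | π = 0.5 | π = 1.0 |
|---|---|---|---|
| 10, 5:5 | 0.044 | 0.030 | 0.007 |
| 10, 4:6 | 0.047 | 0.037 | 0.016 |
| 10, 3:7 | 0.052 | 0.060 | 0.065 |
| 10, 2:8 | 0.066 | 0.105 | 0.200 |
| 20, 6:14 | 0.064 | 0.097 | 0.165 |

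With order assigned at random and not conditioned on the split, the error rate is 0.049 to 0.051 for every n and π tried. Values below 0.05 at or near balance show the other cost: an unmodelled period effect inflates the error SD, so the test loses precision.

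**Step 4: what site-specific balancing gains.** Simulation with 20 participants, 10 per language, spread over two VA bands and JMD. Balancing within strata but across sites gives a mean within-language imbalance of about 0.18. Adding site to the strata lowers it to about 0.07 to 0.08 with blocks of two, and to about 0.11 with blocks of four.

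**The case against.** **The same-day pre-test.** The SAP describes test time as an effect at three times, although four are tested. Its level labels most plausibly mean change from that day's baseline, with a minus sign lost in text extraction. On that reading a stable rise from one day to the next cancels within the day, and π is only the between-day difference in within-session learning. The documents give no size for this. The objection stands: 0.4 must not be applied to the whole session-to-session practice effect. The same reading may also make the language trigger less likely. The SAP expects languages to differ in mean performance, and a difference in level would drop out of a change score.

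**The code lists.** A shared list is as unstated as separate lists. The documents support saying that balance within site is not specified. They do not support saying that it is absent. This stands too.

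**Size.** Average type I error is unaffected. At 7:3 with n = 10 it reaches only 0.065 even with π of 1 SD. Splits as extreme as 8:2 are rare.

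**The remedy.** Two sites by three groups makes six cells. If a language had three cells of three, blocks of two would leave one unpaired person in each. The expected imbalance would then be (¼ × 3 + ¾ × 1)/9 = 1.5/9 = 17%, no better than before. That is a worst case; over realistic cell sizes Step 4 shows the imbalance at least 40% lower (0.18 to 0.11 or less).

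**Stronger readings to avoid.** A reader might infer that the SAP always analyses the languages separately, that VA is the only balancing factor, or that order is confounded with stimulation by design. The documents support none of these. The split is conditional, JMD is balanced as well, and any confounding is partial and arises by chance.

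**Conclusion.** The point holds as a minor gap in specification. Balance of order is not secured at the language level, the SAP may report at that level, and nothing in the models compensates. The harm needs three things together: codes not balanced within site, an unequal split in a language, and a period effect that survives the same-day pre-test. Given those, the per-language contrast carries 0.2 of the remaining period effect at 6:4 and 0.4 at 7:3, and the stimulation-by-language contrast can carry up to twice as much.

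The 17% mean imbalance and the 18% chance of 7:3 or worse rest on 10 per language, equal language sizes and a shared list. At 15 or 20 per language the mean falls to 15% or 12%, and the chance of an imbalance of 0.4 or more falls to about 3%. The result is conditional bias and lost precision. It is not a systematic inflation of type I error.

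**What to change.** 1. **Allocation.** State in step 12 that the blinded codes are prepared separately for Waterloo and Hong Kong, in small blocks within VA band and within JMD at each site. If this is already done, one sentence is enough. The cost is a revised code list and more, smaller strata. With blocks of two, up to one participant per cell stays unpaired.

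2. **Analysis.** And/or add stimulation order as a between-subject factor, with its interaction with stimulation (which carries the period effect), to the combined and per-language models on both routes. Estimate the stimulation effect as the equally weighted mean of the two orders, and carry the same adjustment into the planned pairwise comparisons. This also covers participants already enrolled and any imbalance caused by dropping incomplete cases. The cost is one degree of freedom for the order term, plus some variance when orders are unequal. At 7:3 the variance factor is ¼ × (1/7 + 1/3) = 0.119 against 1/10 = 0.100 at 5:5, about 19% more.

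3. **Reporting.** Give the counts of active-first and sham-first by language among the participants analysed. State explicitly whether each test-time level is a change from the same-day pre-test, since that decides how much period effect can remain.

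### With no Landolt C practice before the first session and no order term in the SAP, practice gain adds noise to the two VA contrasts, and bias only if order is uneven

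*Protocol*

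**What the plan says.** Protocol, "Day 1: Screening and RSVP baseline selection": the visit comprises refraction, a chart acuity test ("Distance ETDRS acuity"), MNREAD, an ocular health check, microperimetry and, for those who qualify, "Full RSVP test [45+ minutes", which crosses five print sizes with five speeds. No Landolt C or FrACT run is listed.

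Protocol, Treatment Days: the Landolt C tests first appear in step 2, "Secondary outcomes pre-test. Computer is fixed 3 meters away". They are repeated during stimulation and at 5 and 30 minutes afterwards. Which of the two comes first is randomised for each participant and then kept. The protocol classes them as secondary and RSVP as primary.

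SAP, Planned Study Components: A.2 defines "Test Time (effect during, effect 5 mins post, effect 30 mins post". The levels beneath it refer to baseline, which I read as each time point relative to the same session's pre-test. B.1 is "2 (Stim type) x 3 (Test time) analysis: Outcome is Crowded VA in logMAR (FrACT", and B.2 treats uncrowded VA in the same way. The active-sham follow-up in Analysis Procedure 2a is paired: "Examine planned comparisons with within-subject ttests". Neither the factors in A nor the seven covariates in D include session or order. E.2 drops anyone with incomplete data.

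Protocol, Day 1 step 12: within two VA groups, active and sham are "to be balanced as far as stimulation schedule". JMD participants are balanced without VA groups.

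**The concern.** The first session's change scores are measured against a participant's first listed exposure to the task, while a later session's are measured against a practised score. If people improve simply by doing the test, the first session shows extra gain whatever the stimulation. A participant who had active stimulation first then looks better on active, and one who had sham first looks better on sham. The SAP has no term to absorb this.

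At stake is the precision of two of the three SAP outcomes. There is also a risk of bias wherever the analysed set does not hold equal numbers of the two orders. RSVP is less exposed because Day 1 already gives long contact with that task.

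**Working it through.** The plan states no sample size, SD, effect size or learning gain, so there is no figure to reproduce. The calculation below shows scale only.

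**Inputs from the documents:** within-participant active-sham contrast; change from the session pre-test; balanced schedules; no order term; complete cases only; two-sided alpha 0.05.

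**Assumed:**
- Two sessions, one active and one sham.
- SD of the active-sham difference without practice: 0.08 or 0.12 logMAR.
- G, the extra practice gain in session 1 over session 2: 0.05 logMAR (range 0.03-0.08), in the direction of improvement.
- For power only: N = 20 and a true effect of 0.06 logMAR.

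**Model.** For participant i, D = tau + s × G + error, with s = +1 if active came first and -1 if sham came first.

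**Step 1, bias.** Bias = G × (n1 - n2)/N, where n1 and n2 are the active-first and sham-first counts. At G = 0.05:
- 10:10 gives 0.05 × 0/20 = 0.
- 12:8 gives 0.05 × 4/20 = 0.010 logMAR.
- 13:7 gives 0.05 × 6/20 = 0.015 logMAR.

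**Step 2, variance in the unadjusted analysis, equal orders.** Share due to practice = G²/(G² + SD²).

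| G | SD 0.08 | SD 0.12 |
|---|---|---|
| 0.03 | 0.0009/0.0073 = 12% | 0.0009/0.0153 = 6% |
| 0.05 | 0.0025/0.0089 = 28% | 0.0025/0.0169 = 15% |
| 0.08 | 0.0064/0.0128 = 50% | 0.0064/0.0208 = 31% |

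At G = 0.05 the variance is multiplied by 0.0089/0.0064 = 1.39 or 0.0169/0.0144 = 1.17.

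**Step 3, effect on the test.** This was a simulation of one paired t-test, 40,000 runs per setting, SD 0.08.
- 10:10 without an order term: moving G from 0 to 0.05 lowers power from 0.89 to 0.80 and type I error from 0.050 to 0.023. The test becomes conservative.
- 13:7 without an order term, G = 0.05: type I error is 0.07.
- With an order term: bias is 0, type I error is 0.048-0.052, and power is 0.89 at 10:10 and 0.85-0.86 at 13:7, whatever G is.

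The simulation gives everyone the same G, so it shows the most that an order term can recover.

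**Step 4, what an order term leaves.** If individual gains vary around their mean with SD v, the remaining share is v²/(v² + SD²).

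| v | SD 0.08 | SD 0.12 |
|---|---|---|
| 0.02 | 0.0004/0.0068 = 6% | 0.0004/0.0148 = 3% |
| 0.025 | 0.000625/0.007025 = 9% | 0.000625/0.015025 = 4% |

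This gives the 3-9% range. At v = 0.03 the shares would be 12% and 6%.

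**The case against.** Several stronger readings are tempting, and the documents do not support them.

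- **That learning biases the active-sham comparison.** Schedules are to be balanced within the VA groups and among JMD participants. With equal orders the gain cancels in the mean (step 1). What stands is that no balance is stated within language, or within most of the covariate levels for which the SAP can trigger separate ANOVAs. The SAP's median split on VA need not match the protocol's VA groups either. Complete-case exclusion can also upset the balance.
- **That a practice run would recover the 15-28%.** That share comes from an average shift whose sign follows order, and an order term removes it. The part for which practice is the only remedy is the smaller one in step 4.
- **That learning is concentrated before the test during stimulation and so hides an early effect.** Nothing in the documents says when learning occurs. Under balanced order the sham sessions carry the same average gain at each time point.
- **That RSVP was deliberately given a familiarisation visit.** The protocol describes Day 1 as screening and selection of the RSVP condition. Any practice is a by-product, and no such selection step is described for Landolt C.
- **That both VA baselines are wholly naive.** Whichever Landolt C test comes second in the pre-test already follows the other, and the Day 1 chart test gives some experience of acuity testing.

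The protocol is also an outline, so its silence on practice trials is weak evidence that none are given. The VA tests are secondary there. These points lower the stakes, but they do not supply an order term.

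**Conclusion.** The point holds as a modest loss of precision on crowded and uncrowded VA, with bias conditional on uneven order in an analysed set. Under the assumed gain of 0.05 logMAR, practice makes up about 15-28% of the variance of the unadjusted difference (6-50% over the full assumed range). An order term would leave about 3-9% under the assumed spread of individual gains. If order were 12:8 or 13:7, the same gain would shift the mean difference by 0.010 or 0.015 logMAR.

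All of these sizes rest on assumed values. If practice is partly lost between treatment days, G is smaller. The documents do not show that G is large, nor by how much one practice run would reduce it. This is an inexpensive improvement; it does not invalidate the planned analysis.

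**What to change.** 1. **Protocol:** add one practice run each of crowded and uncrowded Landolt C, in the participant's randomised order and not analysed. Place it after the Day 1 RSVP test or before the first treatment-day pre-test. Running it before the Day 1 RSVP test risks tiring participants ahead of the test that sets the primary-outcome condition. If the site already gives practice trials, the protocol should say so.
2. **SAP:** add session/order as a factor in the model for the two VA outcomes, in both the parametric and the nonparametric route. Take the planned active-sham comparisons with that adjustment as well, because plain paired tests would leave the order effect in. Report the active-first and sham-first counts for each analysed set and for each separate language or covariate analysis.

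Cost: a few extra minutes (assumed 5-10) and some added fatigue at one visit, on existing equipment, and one degree of freedom in the model. The practice run helps only participants who have not yet started treatment days. The order term can be applied to everyone, provided it is fixed before the active-sham results are seen.
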